Patients will be asked to document their symptoms using the symptom diary card (Appendix 5) as a memory aide. Subjects will be asked to complete a symptom diary card at baseline, prior to FMT, and on the day of treatment to assess their baseline. They will then be asked to complete a symptom diary card each day for 1 week post-FMT and then once a week thereafter for 12 weeks and then during follow-up at weeks 26 and 52. The symptom diary card will help the patient monitor and keep track of adverse events and will be reviewed by the Principal Investigator.

In addition the DSMB may convene additional meetings if necessary to ensure the ongoing monitoring and safety of the subjects treated with FMT. The internal DSMB will include the following individuals: [name] (BWH Gastroenterology, Chair), [name] (Gastroenterology – BWH) and [name] (Pulmonology/Ethics-BWH). All events will be reported directly to the DSMB and the Institutional Review Board (IRB) in accordance with Harvard University policy: Investigators will promptly report to the IRB all unanticipated problems involving risks to human subjects or others under Title 21 of the Code of Federal Regulations (21 CFR) part 56 (Institutional Review Boards), part 312 (Investigational New Drug Application), and part 812 (Investigational Device Exemptions).Harvard Medical School policy is consistent with guidance set forth by the Office for Human Research Protections (OHRP) (presented January 15, 2007) <http://www.hhs.gov/ohrp/policy/AdvEvntGuid.htm> and the FDA (presented January 14, 2009) <http://www.fda.gov/downloads/RegulatoryInformation/Guidances/UCM126572.pdf> when determining what related events require review by the Institutional Review Board. Any serious AEs also will be evaluated by the DSMB for review and determination of whether the trial should continue.

All subjects will be followed for an additional six months following the end of their treatment. Subjects that did not experience a AEs or SAEs will receive a telephone call to monitor their current symptoms and quality of life. For subjects that did experience a AE or SAE that was found to be connected to the FMT treatment, we ask that they return to our medical center for an exam with their gastroenterologist. All treatment and outcome of AEs will be documented on the CRF and summarized in the CSR. All AEs will be followed to resolution or stabilization by the study physician.

VIII. Biostatistical Analysis:

This is an exploratory study as relatively little is known about the microbiome of patients with obesity. Thus, the main objective of our study is to assess the safety of FMT in obese patients. Secondarily we will be able to characterize variability in the microbiome of obese patients to aid

in estimating effect sizes for designing larger studies powered to detect associations between microbiome data and GLP-1 levels and possible weight loss/BMI.

**IX. Risks and Discomforts:
Fecal Microbial Therapy:**

Known Risks of FMT

- Altered bowel pattern (diarrhea, constipation)
- Cramping
- Belching

Potential Risks of FMT

- Transmission of pathogenic bacteria, viruses, fungi
- Transmission of allergens
- Alteration in intestinal metabolism

Privacy and Confidentiality:

This study involves the collection of personal health information. Accidental release of personal health information is a risk of participation in this study. Measures will be taken to protect the confidentiality of all subjects' information. These measures include keeping all information collected about the subjects' confidential, keeping information in locked rooms, and having physicians who are directly involved with a subject's clinical care involved in the study.

Venipuncture: Risks of having blood drawn include pain, bruising, or infection.

Pregnancy: The risks to fetuses and women who are pregnant are unknown.

X. Potential Benefits:

Subjects may not receive any benefits from taking part in this study. However this research and the results of this study may benefit others in the future.

The potential benefits include:

- Restoration of fecal diversity
- Increase in GLP-1 hormones
- Weight loss

[figure not shown]
As this is a pilot study, it is difficult to quantify the expected benefits.

XI. Monitoring and Quality Assurance:

The Principal Investigator, [name], will assure the validity and integrity of the data and adherence to the IRB-approved protocol.

Study staff will review completed CRF's before each visit to ensure completeness of previous entries. Entries that need clarification will be reviewed by the PI, and the subject and/or treating gastroenterologist will be consulted if needed.

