Hypothesis: Fecal microbiota transplantation will result in a sustained repopulation of the patient's microbiome that corresponds to the bacteria from the donor stool.

III. Methods and Study Design

This is a randomized controlled pilot study to assess the safety and to measure the microbiological and clinical impacts of FMT in patients with obesity. We will continue to prospectively enroll and screen adult patients until 20 patients have completed all study visits. We anticipate total enrollment to be 50 patients to account for screen fails and dropouts. Eligible patients are those who are obese (BMI of 35 kg/m² or greater). Patients will be randomized 1:1 to receive FMT or placebo. The participants will receive either an FMT from a lean healthy donor using 30 induction FMT capsules or placebo capsules. The participants will continue to receive a monthly maintenance dose of 12 FMT oral capsules or placebo at week 4 and week 8. Serum for hormone levels will be collected at baseline, weeks 1, 4, 6, 8 and 12. Stool for microbial assessment will be collected at baseline and weeks 1, 4, 6, 8, 12, 26, and 52. A Food Frequency Questionnaire will be taken by the patient at week 0. Donor Stool will be obtained from OpenBiome. OpenBiome is a nonprofit 501(c)(3) organization that provides hospitals with screened, filtered, and frozen material ready for clinical use (See Attachments for OpenBiome Quality and Safety Program as well as donor screening examples).

Primary Safety Endpoint:

Safety Endpoints: Number and nature of adverse events at week 1, 6, 12 and 26.

Primary Clinical Endpoint:

The primary clinical end point is an increase in the AUC for GLP-1 after a mixed meal test from baseline and 12.

Secondary Endpoints:

- Microbial Endpoints: Recipients fecal microbial diversity at week 6 and 12 compared to baseline
- Clinical Endpoints: Decrease in BMI and waste circumference at week 6 and 12 compared to baseline.

Trial Treatment:

The treatment for this trial will be administration of an induction dose of 30 FMT capsules ingested orally. Treatment will occur after screening.

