5. Placebos are quarantined until they have passed bioburden testing, as outlined in section XII below.
6. Doses are transferred into the final pharmaceutical bottle packaging. The dosage size depends upon the requirements of an individual clinical trial's specifications. Clinical trial specifications vary with the trial protocol, objectives, and the indication being targeted.

Labeling

See Drug Master File (15543).

IV. STUDY PROCEDURES

An outline of the study timeline and measurements is shown in Appendix 1

Overview. This is a randomized controlled pilot study to assess the safety of FMT in obese patients. Additionally, the study will measure the microbiological and clinical impacts of FMT in patients with obesity. We will continue to prospectively enroll adult who are obese (BMI of 35 kg/m² or greater) after providing written informed consent until 20 have completed all study visits. We anticipate total enrollment to be 50 patients to account for screen fails and dropouts. The study participants will be randomized 1:1 to either the treatment arm or the placebo arm. The treatment arm will receive an FMT induction followed by monthly (weeks 4 and 8) maintenance oral capsules for 12 weeks. The placebo group will receive placebo capsules at the time of their induction followed by monthly intake of oral placebo capsules for 12 weeks. The participants will not receive dietary instruction and will be asked to continue with their regular diet. Information about their dietary habits will be collected at each study visit. Donor Stool and placebo material will be obtained from OpenBiome. OpenBiome, with whom we have previously collaborated with, is a nonprofit 501(c)(3) organization that provides hospitals with screened, filtered, and frozen material ready for clinical use.

A. Recipient Procedures

Week -2: Screening – potential subjects will undergo the following screening procedures one to two weeks prior to FMT to determine if they meet the recipient selection criteria;

1. Repeat of Medical record review to confirm diagnosis and treatment history if questions remain after initial screen. This will include either review of partner's available data or data provided from home provider (When applicable)
2. Symptom assessment (Symptom Diary Card) and physical exam by study physician
3. Anthropometric measurements: BMI, Iliac measurements, waist-to-hip ratio

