Symptom diary Cards will be filled out weekly for adverse event monitoring

Week 4, 8 (Treatment and Control Arms): Monitored Capsule Consumption and Follow-up study visits for assessment of:

- Ingestion of 12 FMT capsules or inactive placebo.
- A proton pump inhibitor will be taken daily for the 48 hours 24 hours prior to and day of capsule consumption.
- BMI, Iliac measurements, hip to waist ratio
- Stool for microbiome analysis and metabolomics
- CBC, LFTs, FBG, HgA1C, lipids, glucose, metabolomics
- diet recall
- Symptom diary Card and Adverse Event screening

Weeks 6, 12 : Follow-up study visits for assessment of:

- BMI, Iliac measurements, hip to waist ratio
- Stool for microbiome analysis and metabolomics
- CBC, LFTs, FBG, HgA1C, lipids, glucose, metabolomics, ghrelin and leptin, PYY and adiponectin
- Mixed meal tolerance test followed by serum for GLP-1, Leptin and PYY at time 0, 15, 30, 45, and 60
- diet recall
- Indirect Calorimetry
- Symptom Diary Card and Adverse Event screening

Week 26 and 52:

- Safety assessment and Symptom Diary Cards via phone interview by a physician to screen for adverse events.
- Stool sample for microbiome analysis to be mailed in
- Ask for the patients current weight

Stool collection instructions are outlined in Appendix 2.

Patient obligations in the study will end at week 52 however the patient's medical record may be followed prospectively for evaluation of weight loss and weight loss surrogates as well as metabolic parameters done for clinical care through year 5 post-enrollment as needed. This may include review of partner's available records or records from home provider. (when applicable)

Stopping Criteria

Adverse events will be specifically monitored at week 1, 4, 6, 8, 12, 26, and 52 after FMT by direct patient interviews, or by reporting from clinical sites of adverse events at any time in-between. A data safety and monitoring board (DSMB, Appendix 5) will review all patient data to ensure optimal patient safety and precautions for subjects with obesity treated with FMT. A severity grade for adverse events (Appendix 6) and subject symptom diary cards will be used (Appendix 7). The DSMB will meet a minimum of 2 times: after treatment of the first 10 subjects, and after treatment of all 20 subjects. Study will be stopped under the following circumstances;

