- Any unexpected serious adverse events occur that the DSMB determines as at least possibly related to FMT or detection of new pathogenic intestinal infection in stool samples in any patient treated.

Any subject who develops a serious adverse event that is judged to be probably, possibly, or definitely related to FMT therapy will receive no further FMT treatment. They will remain in the trial only for adverse event follow-up.

Accountability Procedures for the Investigational Product

The location, volume and number of all FMT donor solutions will be maintained in a log by the research team. The principal investigator will be responsible for accurate record and tracking of all FMT solutions. Logging of FMT solution used for administration will be performed using a two-person process.

Data to be Recorded Directly on the CRFs

Data will be obtained from patients directly, and their electronic health record as follows;
Demographics , age, gender, co-morbidities, medication use, and laboratory values.

Donor Procedures (OpenBiome):

Prior to enrollment, donors (age >18), receive informed consent with oversight from MIT's IRB and COUHES. Donors are interviewed by a healthcare professional to determine whether they meet the following:

Clinical Exclusion criteria:

1. Infectious risk factors:

- Known HIV, Hepatitis B or C infections or exposure within previous 12 months
- High risk sexual behaviors
- Use of illicit drugs
- Tattoo or body piercing within previous 6 months
- Incarceration or history of incarceration
- Known current communicable disease
- Risk factors for variant Creutzfeldt-Jakob disease
- Travel within previous 3 months to countries where risk of infectious diarrhea is elevated

2. Gastrointestinal and systemic comorbidities:

- History of IBD, irritable bowel syndrome, chronic constipation or chronic diarrhea
- History of gastrointestinal malignancy or known polyposis
- Antibiotic use within the previous 3 months
- Immunosuppressive state or use of immunosuppressive medications
- History of major gastrointestinal surgery (e.g., gastric bypass)
- Metabolic syndrome ; history of NAFLD, hypertension, dyslipidemia, CAD, CHF
- Systemic autoimmunity, e.g., multiple sclerosis, connective tissue disease
- Atopic diseases including asthma and eczema, eosinophilic disorders of the gastrointestinal tract
- Chronic pain syndromes, e.g., chronic fatigue syndrome, fibromyalgia

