to ensure the ongoing monitoring and safety of the subjects treated with FMT. Any serious AEs also will be evaluated by the DSMB for review and determination of whether the trial should continue. An example of the DSMB meeting minutes are at the end of this document. The study will not proceed at each of these time points until the DSMB gives approval to continue.

Safety Reporting

In accordance with applicable policies of the BWH/PHRC Institutional Review Board (IRB), the investigator-sponsor will report, to the IRB, any observed or volunteered Unanticipated Problem that is determined to be 1) unexpected); 2) related or at least possibly related to study participation; and 3) suggests that the research places subjects or others at a risk of unknown harm or addition/increased frequency of harms (including physical, psychological, economic, legal, or social harm) than was previously known or recognized. Unanticipated problems may be adverse events, protocol deviations, noncompliance or other types of problems, but MUST meet all of the criteria listed above. Unanticipated problem reports will be submitted to the IRB in accordance with the respective IRB procedures.

Applicable unanticipated problems will be reported to the IRB as soon as possible and, in no event, later than 10 calendar days following the investigator-sponsor's receipt of the respective information. For Internal Fatal/Life-Threatening Unanticipated Problems, the PI should notify the IRB Chair by phone immediately and consider voluntarily halting subject enrollment.

Follow-up information to reported adverse event will be submitted to the IRB as soon as the relevant information is available. If the results of the investigator's follow-up investigation show that an adverse event that was initially determined to not require reporting to the IRB does, in fact, meet the requirements for reporting; the investigator will report the unanticipated problem to the IRB as soon as possible, but in no event later than 10 calendar days, after the determination was made.

4. Grading and Attribution Methods for Adverse Events

Grading Scale

- 0 No adverse event or within normal limits
- 1 Mild adverse event – did not require treatment
- 2 Moderate adverse event – resolved with treatment
- 3 Severe adverse event – resulted in inability to carry on normal activities and required professional medical attention
- 4 Life threatening or disabling adverse event
- 5 Fatal adverse event

Attribution Scale

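### Enrolment counts 20 completers but the DSMB schedule counts 20 treated, so later-treated patients may have no scheduled review; separately, a related SAE ends a patient's outcome assessments

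*Combined protocol and SAP*

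**What the plan says.** **Enrolment.** Section III (Methods and Study Design) sets the closing rule: "We will continue to prospectively enroll and screen adult patients until 20 patients have completed all study visits". The Overview in Section IV repeats it: "after providing written informed consent until 20 have completed all study visits". Both sections expect losses: "We anticipate total enrollment to be 50 patients to account for screen fails and dropouts". Allocation is fixed at randomisation: "Patients will be randomized 1:1 to receive FMT or placebo".

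**Length of follow-up.** The week 26 and week 52 contacts in Section IV are physician phone interviews with a mailed stool sample. The same section adds: "Patient obligations in the study will end at week 52". The primary clinical endpoint, GLP-1 AUC after a mixed meal, is assessed at week 12.

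**DSMB schedule.** Section IV (Stopping Criteria), Section VII and section 3 of the charter in Appendix 3 all set a minimum of two meetings: "after treatment of the first 10 subjects, and after treatment of all 20 subjects". The charter adds: "The study will not proceed at each of these time points until the DSMB gives approval to continue".

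**Replacement.** Section V (Subject Withdrawal Criteria) provides for replacing withdrawn patients only on the ground that they were not treated.

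**Related SAE.** Under Stopping Criteria, a patient with an SAE judged possibly, probably or definitely related receives no further FMT, and then: "They will remain in the trial only for adverse event follow-up". The same section stops the whole study for an unexpected SAE that the DSMB judges at least possibly related.

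**Analysis.** Section VIII describes an exploratory study with safety as its main objective. It defines no analysis set and no rule for missing data.

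**The concern.** The number 20 does two jobs. In the enrolment rule it counts patients who finish; in the DSMB schedule it counts patients who start. The protocol expects dropouts, so the first count calls for more treated patients than the second allows for. Anyone treated beyond the 20th comes after the last scheduled review, in a study whose main objective is safety.

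The second issue is separate. Restricting a patient to adverse event follow-up after a related SAE ends that patient's mixed meal tests, anthropometry and stool samples from then on. If the event comes before week 12, the primary clinical endpoint is missing. The reason it is missing is a post-randomisation event judged related to treatment, which is the kind of missingness that can bias a comparison between arms. With so few patients, each loss counts.

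**Working it through.** **1. The plan's own figures.** Neither 20 nor 50 can be reproduced. The documents give no effect size, standard deviation, power, screen-failure rate or dropout rate. Only the implied completion can be derived: 20/50 = 40%. That is compatible with very different numbers treated, using treated = 50 × (1 − screen-failure share) and dropout = 1 − 20/treated:

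| Screen-failure share | Treated | Dropout after treatment |
|---|---|---|
| 60% | 20 | 0% |
| 50% | 25 | 20% |
| 40% | 30 | 33% |
| 0% | 50 | 60% |

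Only the first row matches the DSMB's count of 20 treated.

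**2. Dropout alone.** Let d be the share of treated patients who do not complete all visits (assumed). Treated patients needed for 20 completers = 20/(1 − d), rounded up. The chance that at least one of the first 20 treated drops out, so that more than 20 must be treated, is 1 − (1 − d)^20.

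| Assumed d | 20/(1 − d) | Treated | Chance that more than 20 are needed |
|---|---|---|---|
| 0% | 20.0 | 20 | 0% |
| 5% | 21.1 | 22 | 64% |
| 10% | 22.2 | 23 | 88% |
| 20% | 25.0 | 25 | 99% |

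**3. Dosing during follow-up.** Read literally, enrolment stays open until the 20th completer finishes. The extra patients are accrual per month × follow-up in months. Twelve weeks is 84/30.44 = 2.76 months; 52 weeks is 364/30.44 = 11.96 months. With no dropout, an assumed one patient dosed per month and no pause in dosing, 20 + 2.76 is about 23 treated if completion means week 12, and 20 + 11.96 is about 32 if it means week 52. So the overshoot does not depend on dropout.

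**4. The related-SAE rule.** Twenty completers randomised 1:1 give about 10 per arm, so one lost patient is 1/10 = 10% of an arm. How often this would happen is not stated. The chance of at least one related SAE among 10 FMT patients is 1 − (1 − p)^10: 10%, 18%, 40% or 65% at assumed per-patient rates p of 1%, 2%, 5% or 10%. Only events before week 12 affect the week 12 GLP-1 AUC, and only those before week 6 also affect the week 6 data.

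**The case against.** **Oversight does not end at 20.** Two meetings is a minimum, extra meetings are allowed, all events are reported to the DSMB, and each serious adverse event is evaluated for whether the trial should continue (Section VII and the charter). This stands. Patients after the 20th lack a scheduled meeting, not oversight, and about half of them receive placebo. But extra meetings are discretionary and SAE review is triggered by events; neither is a planned look at cumulative non-serious events.

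**The overshoot may be small.** A reader might combine 20% dropout with one to three patients dosed per month and arrive at 28 to 33 treated on the week 12 reading, or 37 to 61 on the week 52 reading. The documents support none of these as an estimate: accrual and dropout are both assumed, dosing is taken as uninterrupted despite the charter's hold at each review, and 61 exceeds an anticipated total of 50 that includes screen failures. Section IV uses the word visits for weeks 4 to 12, whereas weeks 26 and 52 are remote contacts, so week 12 is a natural meaning of completion. Against that, obligations run to week 52 and the text does not settle the matter.

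**A completer-only GLP-1 result is not stated.** A reader might infer that the GLP-1 result will come from completers selected for tolerability. Sections III and IV say when enrolment ends, not who is analysed, and no text excludes a patient who has a week 12 test but misses a later contact. Nor is ordinary dropout said to be driven by tolerability. Data collected before an SAE are not discarded. If the analysis were limited to completers, with 20% of one arm lost on a tolerability measure correlated 0.2 to 0.5 with GLP-1 change, the shift would be 0.350 × 0.2 = 0.07 to 0.350 × 0.5 = 0.18 SD, where 0.350 is the normal density at the 20% cut (0.280) divided by 0.8. The standard error with 10 per arm is √(2/10) = 0.45 SD.

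**The SAE route is narrow.** An unexpected, possibly related SAE stops the study, so enrolment continues past such a patient mainly when the event was expected. Section IX lists only altered bowel pattern, cramping and belching as known risks. This stands and limits how often the rule would apply.

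**A completer target is defensible** in an exploratory pilot. This also stands; the target need not be dropped.

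**Conclusion.** The point holds in two limited parts.

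First, the enrolment rule and the DSMB schedule contradict each other on what 20 counts. They agree only with no dropout after treatment and no dosing past the 20th patient, and the protocol itself expects dropouts. Some patients are therefore likely to be treated after the last scheduled review. How many cannot be derived from the documents; modest assumed dropout already adds two to five, and continued dosing during follow-up would add more.

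Second, the rule after a related SAE makes later outcome data missing for a reason tied to treatment. The size is about a tenth of an arm per affected patient, at an unknown and probably low frequency.

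The documents do not support saying that the GLP-1 result is a completer-only result, that collected data are thrown away, or that later patients go unmonitored.

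**What to change.** 1. In Sections III, IV, V and VII and the charter in Appendix 3, state whether 20 counts treated or completing patients, and whether completion means week 12 or week 52. Reconcile the replacement wording in Section V with that answer. The completer target itself may stay. Cost: wording.
2. In Section IV (Stopping Criteria), Section VII and the charter, tie the final scheduled DSMB review to the last participant treated rather than to a fixed 20. Cost: possibly one more meeting.
3. In Section IV (Stopping Criteria), leave the treatment-stopping rule untouched. Replace the restriction to adverse event follow-up with a statement that participants who stop treatment may, with consent, continue the scheduled mixed meal, anthropometric and stool assessments, and say in Section VIII that they are analysed in their randomised arm. Cost: a few extra visits.

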The main mechanism of action of GLP-1 is to increase glucose-mediated insulin release, delaying gastric emptying, and inhibiting glucagon release. GLP-1 agonists have been shown to promote satiety¹⁵, leading to weight loss. GLP-1 is secreted within minutes of food intake by L-cells, located in the distal ileum and colon. Oral (but not IV) glucose administration causes GLP-1 secretion¹⁶. Additionally, GLP-1 readily crosses the blood brain barrier where it is thought to regulate ingestive behavior in the hypothalamus, which subsequently has direct effects on gastric emptying and resultant satiety¹⁵. GLP-1 is secreted 15 to 30 minutes after food intake and is there measured at multiple time points post-prandial¹⁷. Additionally, GLP-1 has been shown to increase following other weight loss interventions such as gastric bypass, with significant changes seen as early as 6 weeks¹⁷.

This connection has led to attempts at manipulations of the gut microbiome in order to modulate this process¹⁸. In a recent trial, obese diabetic patients received a fecal microbiota transplantation (FMT) from either lean donors or autologous stool¹⁹. Those in the treatment group were noted to have improved peripheral and hepatic insulin sensitivity. FMT involves the transfer of donor stool to a recipient. It has become widely accepted as a treatment for recurrent *Clostridium difficile* infection (CDI), with a cumulative cure rate of >90% and minimal adverse events²⁰. These preliminary studies suggest that FMT using lean donor stool may be

used to treat obesity and its sequela. **We hypothesize that for obese patients, induction and maintenance FMT utilizing lean donor stool will correct a dysbiosis that has led to a decrease in circulating GLP-1 which acts as a surrogate marker for weight loss.**

II. SPECIFIC AIMS

Specific Aim 1: Assess the safety of FMT in patients with obesity.

Hypothesis: Induction FMT followed by weekly maintenance capsule FMT will be safe and well tolerated by obese patients.

Specific Aim 2: Assess GLP-1 as a therapeutic biomarker for clinical response to fecal microbiota transplantation

Hypothesis: Fecal Microbiota Transplantation will lead to an increase in SCFA which will lead to an increase in the metabolic regulator GLP-1.

Specific Aim 3: Determine the impact of fecal microbiota transplantation on the intestinal microbiome of patients with obesity via 16s ribosomal RNA sequencing.

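### The primary safety endpoint is an event total with no planned analysis, so the main objective gets no estimate of the share of patients affected or of its uncertainty

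*Combined protocol and SAP*

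**What the plan says.** Aim 1 (Section II) hypothesises that FMT "will be safe and well tolerated by obese patients". Section VIII gives safety first place: "Thus, the main objective of our study is to assess the safety of FMT in obese patients". The endpoint that serves this aim, in Section III, is "Safety Endpoints: Number and nature of adverse events at week 1, 6, 12 and 26".

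On size, Section III enrols "until 20 patients have completed all study visits" and adds: "We anticipate total enrollment to be 50 patients to account for screen fails and dropouts". On allocation: "Patients will be randomized 1:1 to receive FMT or placebo".

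On data capture, Section VII asks patients to "complete a symptom diary card each day for 1 week post-FMT and then once a week thereafter for 12 weeks", and Section IV says "Symptom diary Cards will be filled out weekly for adverse event monitoring". Section VII describes the card as an aid to recall that the principal investigator reviews. The card in Appendix 5 has columns for onset and resolution dates. Adverse events are also sought by interview, recorded on the CRF and summarised in the study report; the unit of that summary is not stated.

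Section VIII contains no safety denominator, patient-level proportion, confidence interval, between-arm comparison or acceptable rate.

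**The concern.** Whether FMT is safe and tolerable in obese patients is a question about patients: what share of those dosed has a problem, how severe it is, and how sure we can be. A number of events does not answer it. Events cluster within people, so in a small arm one or two symptomatic patients can supply most of the total, and two arms with similar totals can have very different numbers of patients affected.

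The time points are also loose. The endpoint does not say whether the counts at the four weeks are cumulative, new since the last visit, or ongoing, so a long-lasting event could count once or several times.

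At stake is the trial's main objective. Without a planned proportion and interval, a report of no serious events could be read as support for the Aim 1 hypothesis with no statement of how large a risk remains possible.

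**Working it through.** **Is there a planned figure to reproduce?** No. The 20 completers come with no alpha, power, event rate, margin or target precision.

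**Inputs from the documents.** 20 completers, randomised 1:1, so 20/2 = 10 FMT completers. Anticipated enrolment is 50, which includes screen failures and dropouts, so at most 50/2 = 25 FMT patients. The number dosed is not stated; 10 to 25 is used below as an assumed range.

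**Step 1: what an event total says about patients.** If an arm of 10 has E events in total (E at least 1), the number of affected patients X can be anything from 1 to the smaller of E and 10. Take E = 10 as an assumed total:
- X = 1: 10% affected, exact 95% interval 0.25% to 44.5%.
- X = 10: 100% affected, with lower limit 0.025^(1/10) = 69.2%.

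The two intervals do not overlap, yet the total is the same. Only for E = 0 or E = 1 does the total fix the number of patients.

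**Step 2: what a patient-level endpoint gives (Clopper-Pearson, n = 10).**
- 0/10, one-sided upper limit: 1 − 0.05^(1/10) = 25.9%.
- 0/10, two-sided upper limit: 1 − 0.025^(1/10) = 30.8%.
- 1/10: 0.25% to 44.5%.
- 2/10: 2.5% to 55.6%.

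**Step 3: sensitivity to the number dosed (zero events, two-sided, 1 − 0.025^(1/n)).**

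| FMT patients dosed (assumed) | Upper 95% limit |
|---|---|
| 10 | 30.8% |
| 15 | 21.8% |
| 20 | 16.8% |
| 25 | 13.7% |

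**Step 4: chance of seeing any affected patient among 10, 1 − (1 − p)^10.** At a true risk p of 5% it is 40%; at 10%, 65%; at 20%, 89%. So a true 10% risk would show no affected patient in 100% − 65% = 35% of such trials.

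**The case against.** The strongest defence is that this is an exploratory pilot. The endpoint wording does not forbid a patient-level table, no decision depends on an adverse event rate, and the stopping rule in Section IV acts on a single qualifying event. Much of that stands and limits the weight of the point. It does not remove it: the wording does not require the table either, the stopping rule estimates no risk, and a pilot whose main objective is safety should produce an estimate with its uncertainty.

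Three stronger readings are tempting, and the documents do not support them.

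- *Every diary entry counts as an event, so one symptom could count up to 19 times.* There are 7 daily plus 11 or 12 weekly cards, hence 18 or 19 after induction to week 12. But nowhere is an entry equated with an event, and the worked example in Appendix 5 records a three-day fever as one row. What remains is that Appendix 5 also asks for each symptom's worst level each day, and no rule says when repeated entries are one episode.
- *The comparison between arms has an inflated false-positive rate.* Under assumed conditions (mean of 3 events per patient, 10 per arm, no true difference), a test on pooled totals rejects in about 18% of trials with moderate between-patient variation (gamma shape 2) and 30% with more (shape 1), against 3.6% if events are independent. The plan contains no such test, and the mean and shapes have no source in the documents. These rates are hypothetical and should not be cited against the plan.
- *The endpoint as written makes a bound impossible.* Zero events means zero patients with events, so the limits for a clean result can be computed from it. That bound is absent because Section VIII plans no interval. The unit of counting becomes an obstacle from two events upward.

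**Conclusion.** The concern holds as an under-specified endpoint for the trial's main objective. The plan names a number of events, gives no safety analysis, and so commits to no estimate of the share of patients affected and no measure of its uncertainty. Followed literally, it yields totals that a few patients can dominate.

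The patient-level alternative is informative but wide. With zero serious events among 10 FMT patients, risks up to 26% (one-sided) or 31% (two-sided) are not excluded; if 25 were dosed, the two-sided limit would be about 14%. The lower figure of 10 assumes that the 20 completers split evenly and that nobody else was dosed. The larger numbers are assumptions, bounded above by half the anticipated enrolment.

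This is a cheap and worthwhile improvement. It does not show that the safety data will be wrong or that a planned test is invalid.

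**What to change.** Reword the primary safety endpoint in Section III and add a short safety analysis to Section VIII:

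1. Endpoint: number and proportion of dosed patients with at least one treatment-emergent adverse event, shown for any event, by worst grade, related, and serious.
2. Denominator: everyone who took at least one study dose, not only completers, because patients who leave early may be those with events.
3. Presentation: by arm, cumulative to weeks 1, 6, 12 and 26, with exact 95% intervals for each arm and for the difference.
4. Counting rule: a continuing episode counts once, identified from the onset and resolution dates already on the diary card.
5. Event totals stay as a descriptive supplement.
6. State the Aim 1 conclusion with the upper confidence limit for the number actually dosed, instead of as a bare statement that the treatment is safe.

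Cost: endpoint wording, one more table and a more modest safety claim. No new data, visits or patients are needed.
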